### Secondary Outcomes (6 months):

- Monocular UDVA, UIVA, UNVA (logMAR).
- Monocular and binocular CDVA, CIVA, CNVA.
- Manifest and objective spherical equivalent refraction.
- Binocular defocus curve performance.

- Halo and glare scores (NEI-RQL-42 items 17 and 38; 0–100 scale).

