## Objectives

**Primary Objective:** To compare binocular uncorrected distance, intermediate, and near visual acuity and patient satisfaction at 6 months among monofocal, enhanced monofocal, and EDOF IOLs.

**Secondary Objectives:** To compare monocular and binocular corrected acuities, refraction, defocus curve performance, and halo/glare symptoms among the three IOL groups.

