## Surgical Technique and Postoperative Care

Standard phacoemulsification using manufacturer-recommended injector systems. IOL power selected to target approximately -0.25 D (first myopic-leaning power). Postoperative regimen: topical 0.5% moxifloxacin + 0.1% dexamethasone five times daily for one week, tapered over three weeks. Follow-up at 1 day, 1 week, 1 month, 3 months, and 6 months.

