## Assessments and Outcome Measures

At 6 months, visual acuity measured at distance (6 m), intermediate (66 cm), and near (40 cm) under photopic conditions, converted to logMAR. Refraction (manifest and objective), binocular defocus curves (+1.00 D to -2.50 D in 0.50 D steps), and patient questionnaires on halos/glare and spectacle independence were recorded.

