## **Descriptive Statistics**

Continuous variables summarized as mean  $\pm$ SD. Categorical variables summarized as counts and percentages.

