## **Comparative Analyses**

- Kruskal–Wallis tests with Dunn–Bonferroni post hoc comparisons for non-normally distributed continuous outcomes.
- One-way ANOVA with Tukey HSD for key binocular outcomes when appropriate.
- Chi-square or Fisher’s exact tests for categorical variables.
- GEE model with exchangeable correlation structure for binocular UIVA to account for within-subject correlation.

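### Refraction is compared only for location of signed spherical equivalent, so a lens that misses the common -0.25 D target more widely in both directions would test as no different

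*Combined protocol and SAP*

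**What the plan says.** - **Outcome.** The protocol's list of secondary outcomes gives refraction as "Manifest and objective spherical equivalent refraction". No section defines deviation from target, prediction error or the share of eyes within a dioptre band.
- **Purpose.** The secondary objective is "To compare monocular and binocular corrected acuities, refraction, defocus curve performance, and halo/glare symptoms among the three IOL groups". Accuracy against target is not named as an aim.
- **Target.** Surgical Technique and Postoperative Care has "IOL power selected to target approximately -0.25 D (first myopic-leaning power", one rule for all three lenses.
- **Data.** Assessments and Outcome Measures lists "Refraction (manifest and objective), binocular defocus curves" at 6 months. The predicted refraction for the implanted power is not listed.
- **Summary.** SAP, Descriptive Statistics: "Continuous variables summarized as mean $\pm$ SD".
- **Tests.** SAP, Comparative Analyses: "Kruskal–Wallis tests with Dunn–Bonferroni post hoc comparisons for non-normally distributed continuous outcomes" and "One-way ANOVA with Tukey HSD for key binocular outcomes when appropriate". Neither line names SE. GEE is specified there only for binocular UIVA, although Analysis Population says that both eyes contribute and that GEE covers inter-eye correlation in selected analyses.

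**The concern.** SE has a sign and, in this study, a target. Two features of a lens group then matter: whether its average sits on target, and how far individual eyes fall from it. The planned tests address only the first. If half of a group's eyes end at -0.75 D and half at +0.25 D, the mean is -0.25 D although every eye is 0.50 D off. A location test against a tightly clustered group with the same mean has nothing to find.

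What is at stake is how the primary results are read. The primary acuities are uncorrected and the satisfaction scores concern vision without spectacles, so both depend on residual refractive error. The design is a retrospective comparison without randomisation, and the SAP plans no adjustment of acuity for refraction. The refraction comparison is thus a main check on whether an acuity difference reflects lens optics or refractive misses. A non-significant result on signed SE could be taken as comparable refraction when only the averages were comparable.

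**Working it through.** **The plan's own figures.** The plan gives no figure for the spread of SE, so there is nothing to reproduce on this point. Its one computed figure, the post hoc power of 0.96, does not enter here. (By the noncentral F distribution, f = 0.25 and N = 197 in three groups give 0.887, which is a separate matter.)

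**Inputs.** From the documents: target -0.25 D, three groups, total n = 197, two-sided 0.05. Assumed, because the documents are silent: the SDs of SE, normal distributions, a 66/66/65 split, and one independent SE value per unit of n.

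**Step 1: what spread means for accuracy.** For a group centred on target:

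- mean absolute deviation = SD × √(2/π)
- share within ±0.50 D = 2Φ(0.50/SD) − 1

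| Assumed SD (D) | Mean absolute deviation (D) | Within ±0.50 D |
|---|---|---|
| 0.25 | 0.20 | 95% |
| 0.30 | 0.24 | 90% |
| 0.45 | 0.36 | 73% |
| 0.50 | 0.40 | 68% |
| 0.60 | 0.48 | 60% |

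The mean and median signed SE are -0.25 D in every row.

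**Step 2: what the tests would find.** Rejection rates over 3,000 simulated studies per scenario, all groups centred on -0.25 D:

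| SDs by group (D) | Signed SE, Kruskal–Wallis | Signed SE, ANOVA | Absolute deviation, Kruskal–Wallis | Absolute deviation, ANOVA |
|---|---|---|---|---|
| 0.30/0.30/0.30 | 4.6% | 5.4% | 5.3% | 5.0% |
| 0.30/0.30/0.45 | 4.7% | 4.9% | 71.8% | 88.8% |
| 0.30/0.30/0.60 | 5.5% | 5.8% | 99.2% | 100% |
| 0.25/0.25/0.50 | 5.6% | 6.4% | 99.3% | 100% |

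Simulation error near 5% is about √(0.05 × 0.95/3000) = 0.4 percentage points. Tests of signed SE stay close to the nominal 5% whatever the difference in spread.

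**Step 3: the converse.** With equal SDs of 0.30 D and one lens shifted by -0.20 D (means -0.25, -0.25 and -0.45 D), Kruskal–Wallis rejects in 97% of runs on signed SE and in 26% on absolute deviation. The two measures answer different questions, and neither replaces the other.

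**The case against.** The strongest reply is that the plan never sets out to measure accuracy: the objective asks for refraction to be compared, and the target appears under surgical technique, not as an endpoint. That stands. The case for the addition rests on the common target together with uncorrected primary outcomes, not on a promise the plan fails to keep.

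A reader might infer that signed SE cannot show how well a lens reached its target. The documents do not support that. The mean set against -0.25 D shows systematic bias, and the reported SD shows spread. In the half-and-half example above, the SD would be about 0.50 D and visible in the table. The information is untested, not absent.

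A reader might also infer that signed SE should be replaced or kept as description only. That would weaken the plan. Direction matters because intermediate and near acuity are primary outcomes alongside distance acuity, and residual myopia does not affect the three alike. Step 3 shows the loss.

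Third, it might be inferred that any acuity gap would be wrongly credited to lens optics. The secondary outcomes include corrected acuities and defocus curves, which bear on optics, so that goes too far.

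Finally, the documents give no reason to expect unequal spread under one targeting rule, and they assign no test to SE by name. Both are fair. However, both methods offered for continuous outcomes are location tests, so the gap exists whichever is used.

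**Conclusion.** The point holds in a limited form. A difference between lenses in spread around the target would not be detected by the planned comparison of SE: rejection stays at about 5 to 6% under every unequal-SD scenario tried, while absolute deviation is detected in 72% to 100%. The reported SDs would show such a difference descriptively, without a test and without reference to the target.

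These rates rest on assumed SDs, normality, exact centring on target and an even split. They show the mechanism and do not predict this study's data. They also come from Kruskal–Wallis and ANOVA on independent values, so they do not give the power of an analysis that allows for paired eyes.

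This is an inexpensive improvement to a secondary outcome that helps in reading the primary ones. It does not invalidate the primary comparisons.

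**What to change.** 1. **Keep** signed manifest and objective SE as compared outcomes.
2. **Add to Secondary Outcomes:** (a) the absolute deviation of 6-month manifest SE from target, per eye; (b) the percentage of eyes within ±0.50 D of target. Take the target as each eye's predicted SE where the chart holds it, and otherwise as -0.25 D, stated to be an approximation. State how many eyes use each.
3. **Add to Comparative Analyses:** compare (a) and (b) across lenses by GEE with the patient as cluster, extending to these eye-level outcomes a method the SAP already uses.
4. **Report** these beside the mean and SD of signed SE, so that bias and spread are read together.

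**Cost.** SAP wording, one derived variable with its within-band percentage, and a few more secondary comparisons. No new visits or measurements are needed if the fallback is used. Predicted SE is not listed as recorded, so the fallback may be needed for many eyes. Because power was chosen by a myopic-leaning rule, the intended SE varies between eyes, and the fallback mixes that offset with the error.

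**Limit.** This does not adjust the acuity comparisons for refraction. It only lets the reader judge whether the groups reached target equally well.

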## Exclusion Criteria

- Preoperative corneal astigmatism  $\geq 1.0$  D.
- Axial length  $\leq 21$  mm or  $\geq 26$  mm.
- Prior intraocular or corneal surgery.
- Ocular comorbidities affecting vision (severe dry eye, amblyopia, ocular surface disease, corneal pathology, retinal diseases, uveitis, glaucoma, pseudoexfoliation, pterygium).
- Intraoperative or postoperative complications, or failure to complete 6-month follow-up.

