### Primary Outcomes (6 months):

- Binocular UDVA, UIVA, UNVA (logMAR).
- Patient satisfaction scores for distance, intermediate, and near spectacle-free vision (0–10 scale).

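### Refraction is listed as an outcome only as spherical equivalent, so a lens-group difference in residual cylinder could pass for a lens effect, mainly on uncorrected distance acuity

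*Combined protocol and SAP*

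**What the plan says.** The primary acuity outcomes are uncorrected and binocular: "Binocular UDVA, UIVA, UNVA (logMAR") at 6 months. Three places in the protocol deal with refraction, and they do not have the same scope:

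- **Objectives:** a secondary objective is "To compare monocular and binocular corrected acuities, refraction, defocus curve performance, and halo/glare symptoms among the three IOL groups". Refraction is not limited to spherical equivalent here.
- **Assessments and Outcome Measures:** the 6-month data include "Refraction (manifest and objective), binocular defocus curves", again without that limit.
- **Secondary Outcomes:** the listed outcome is "Manifest and objective spherical equivalent refraction". Cylinder, residual astigmatism and vector components do not appear.

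Astigmatism is limited only at entry: under Exclusion Criteria, "Preoperative corneal astigmatism" of 1.0 D or more is excluded. The target refraction is about -0.25 D for all three lenses (Surgical Technique and Postoperative Care).

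The study is a retrospective, non-randomised case series (Study Design). The SAP's Comparative Analyses section lists Kruskal–Wallis, one-way ANOVA, chi-square or Fisher's exact tests, and one GEE model for binocular UIVA whose stated purpose is within-subject correlation. It names no covariate.

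**The concern.** Spherical equivalent is sphere plus half the cylinder, so eyes with quite different cylinder can share one value. A table showing equal spherical equivalents for the three lenses would invite the reader to conclude that their refractive results match, when the uncorrected blur could still differ.

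Nothing in the design balances cylinder across lenses, and nothing in the analysis adjusts for it. If one lens group had more residual cylinder at 6 months for reasons unrelated to the lens, its uncorrected acuity would be worse and the planned tests would attribute the difference to the lens. If the groups are balanced, showing that would strengthen the lens comparison.

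**Working it through.** The plan gives no figure for cylinder, so there is none to reproduce. The check asks what spherical equivalent hides, and how large the consequence could be.

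**Inputs from the documents:** target -0.25 D; test distances 6 m, 66 cm and 40 cm; n = 197 in three groups; alpha 0.05.

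**Assumptions, not in the documents:** eyes on target; mean cylinder 0.50 D in one group against 0.75 D in another; 0.2 to 0.4 logMAR lost per dioptre of blur; acuity SD 0.10 (0.15 also shown); about 66 patients per group (197/3 = 65.7).

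**Step 1. What spherical equivalent hides.** SE = sphere + cylinder/2. Both -0.25 DS and +0.25/-1.00 give SE = -0.25 D. Blur strength at distance is sqrt(SE² + (C/2)²). At SE = -0.25 D:

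| Cylinder C (D) | Distance blur (D) |
|---|---|
| 0 | 0.25 |
| 0.50 | 0.35 |
| 0.75 | 0.45 |
| 1.00 | 0.56 |

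**Step 2. A 0.25 D difference in mean cylinder, by test distance.** The spherical term becomes the eye's defocus at that distance: 0.25 D at 6 m (treated as infinity), 1/0.66 - 0.25 = 1.27 D at 66 cm, and 1/0.40 - 0.25 = 2.25 D at 40 cm. This takes an eye without extended focus.

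| Distance | Blur, C = 0.50 | Blur, C = 0.75 | Added blur | At 0.2 to 0.4 logMAR per D |
|---|---|---|---|---|
| 6 m | 0.354 D | 0.451 D | 0.097 D | 0.019 to 0.039 |
| 66 cm | 1.290 D | 1.320 D | 0.030 D | 0.006 to 0.012 |
| 40 cm | 2.264 D | 2.281 D | 0.017 D | 0.003 to 0.007 |

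**Step 3. Against what the study can detect.** The smallest Tukey-significant pairwise difference is 2.362 × SD × sqrt(2/66): 0.041 logMAR at SD 0.10 and 0.062 at SD 0.15. At SD 0.10 the distance shift is about half to nearly all of that.

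**Step 4. False rejection at distance.** Shift one group by d with no true lens effect. Then Cohen's f = d × sqrt(2)/(3 × SD), and the noncentral F distribution with n = 197 gives:

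| Shift d (logMAR) | SD 0.10 | SD 0.15 |
|---|---|---|
| 0.02 | f = 0.094, rejects 20% | f = 0.063, rejects 11% |
| 0.04 | f = 0.189, rejects 65% | f = 0.126, rejects 33% |

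The nominal rate is 5%. The result depends heavily on the assumptions. With a mean cylinder difference of only 0.10 D and a loss of 0.05 logMAR per dioptre of cylinder, d = 0.005 and the test rejects in about 6% of studies at SD 0.10.

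**The case against.** The strongest case on the other side has five parts.

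**The gap is narrow.** Refraction is unrestricted in the objectives and in the assessments. A reader might infer that the whole plan treats refraction as spherical equivalent, or that cylinder was not measured. The documents support neither; the restriction sits in one line of the outcome list. A reader might also infer that refractive blur would go wholly unseen. That is too strong, because "Monocular and binocular CDVA, CIVA, CNVA" are also secondary outcomes, and uncorrected set against corrected acuity would show blur indirectly. No such contrast is planned, however, and it would not separate cylinder from sphere.

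**The entry rule limits the size.** One corneal limit and one refractive target apply to all three lenses. This stands, and it makes the 1.00 D row an edge case. It does not remove the concern: the limit is on preoperative corneal astigmatism, not postoperative refractive cylinder, and groups can differ below 1.0 D.

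**The imbalance is assumed.** If cylinder were spread evenly from 0 to 1 D, its SD would be 1/sqrt(12) = 0.29 D, and a 0.25 D difference in means would be 0.25/0.29, or about 0.87 SD. The documents give no reason for lens choice to follow cylinder that closely. This stands: 0.25 D illustrates a large imbalance.

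**The effect is mainly at distance.** A reader might carry the distance figure over to UIVA and UNVA. Step 2 does not support that for an eye without extended focus. It could be larger where extended focus reduces the defocus, which the documents do not allow one to compute. Nor do they support any statement that cylinder itself widens the range of vision.

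**Adjustment has its own problem.** Six-month refractive cylinder is measured after implantation. If the lens contributes to it, adjusting for it removes part of the lens effect. Kruskal–Wallis and one-way ANOVA also take no covariate, so a separate model is needed. Both points stand and shape the fix.

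The absence of adjustment is indeed general to the plan. Cylinder still merits its own line, because the listed refraction outcome could give false reassurance on it.

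**Conclusion.** The concern holds in limited form. Equal spherical equivalents across lenses would not show equal refractive blur, and with non-random lens allocation and no covariates a difference in residual cylinder could be mistaken for a lens effect, mainly on UDVA. The size is about 0.02 to 0.04 logMAR at distance and about 0.01 or less at intermediate and near. It rests on an assumed 0.25 D imbalance, an assumed 0.2 to 0.4 logMAR per dioptre of blur, eyes on target and no extended focus; with smaller inputs the effect is trivial.

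A reader might infer that the groups do differ in cylinder and that the primary comparison is biased. The documents contain no cylinder data and do not support that. The point is that the plan, as written, would not find out, while the recorded refraction probably could.

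**What to change.** **Protocol, Secondary Outcomes.** Beside spherical equivalent, add: *manifest refractive cylinder at 6 months (magnitude, and J0 and J45 power-vector components), by lens group.*

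**SAP, Comparative Analyses.** Keep the planned tests and add: *As sensitivity analyses, binocular UDVA, UIVA and UNVA will each be analysed in a linear model on lens group, (a) with the two-eye mean of preoperative corneal astigmatism as baseline covariate, and (b) with the two-eye mean of 6-month refractive cylinder as covariate. We will state whether the lens difference persists in each.*

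Model (a) uses a pre-implantation measure, so it cannot remove any part of a lens effect, but it misses surgically induced change. Model (b) captures residual cylinder directly but conditions on a post-implantation measure, so it must be labelled supportive only.

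**Cost.** One extra table row and two sensitivity models per acuity. No new measurements are needed, provided that the recorded refractions include cylinder, as their unrestricted description implies, and that the corneal values used for the exclusion were kept.

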## **Significance Threshold**

Two-tailed  $p \leq 0.05$  considered statistically significant.

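### Any secondary result at p ≤ 0.05 may be called significant with no control across outcomes, and the eight-level defocus curve has no assigned analysis

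*Combined protocol and SAP*

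**What the plan says.** The protocol's list of secondary outcomes contains:

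- "Monocular UDVA, UIVA, UNVA (logMAR": three outcomes.
- "Monocular and binocular CDVA, CIVA, CNVA": three distances, each monocular and binocular, so six outcomes.
- "Manifest and objective spherical equivalent refraction": two outcomes.
- "Halo and glare scores (NEI-RQL-42 items 17 and 38; 0–100 scale": two outcomes.
- "Binocular defocus curve performance": one entry, with no summary measure and no statement of how many tests it implies.

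The Assessments section describes "binocular defocus curves (+1.00 D to -2.50 D in 0.50 D steps".

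In the SAP, Comparative Analyses gives Kruskal–Wallis tests with Dunn–Bonferroni "post hoc comparisons for non-normally distributed continuous outcomes", ANOVA with Tukey for some binocular outcomes, chi-square or Fisher tests for categorical data, and a GEE for binocular UIVA. The defocus curve is not mentioned there. Under Significance Threshold, any two-tailed p of 0.05 or less is "considered statistically significant", with no distinction between primary and secondary outcomes. Neither document gives a testing hierarchy, an adjustment across outcomes or defocus levels, or a statement that secondary results are exploratory.

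**The concern.** There are two linked gaps.

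First, the single threshold allows every secondary result to carry the label significant on its own p-value. The corrections that are planned protect only the choice among three lens pairs once an outcome has been picked. They do nothing about the number of outcomes examined.

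Second, the defocus curve is a repeated measure: each patient supplies eight correlated acuities. None of the listed methods is assigned to such data. The listed tests for continuous outcomes take one value per patient, so they could be applied to the measured curve only one level at a time. (A scalar summary would also fit them, but none is defined.) Level-by-level testing ignores the dependence between levels, adds eight unadjusted tests, and gives no overall test of whether the curves differ in height or shape. Defocus performance is a stated secondary objective, so isolated levels below 0.05 could be reported as lens differences when they are chance.

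**Working it through.** The documents state no familywise error rate, so there is no plan figure to reproduce. The post hoc power in the Sample Size section concerns a single ANOVA and does not bear on this point.

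**Count of tests**

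- Defocus levels: +1.00, +0.50, 0, −0.50, −1.00, −1.50, −2.00 and −2.50 D, so 8.
- Each level tested: 3 + 6 + 2 + 2 + 8 = 21 omnibus tests.
- Curve treated as one test: 3 + 6 + 2 + 2 + 1 = 14.

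**Independent outcomes, no true lens difference**

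P(at least one p ≤ 0.05) = 1 − 0.95^m.

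- m = 21: 1 − 0.95^21 = 0.659
- m = 14: 1 − 0.95^14 = 0.512
- m = 8 (defocus levels alone): 1 − 0.95^8 = 0.337

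The expected number of false positives does not depend on correlation: 21 × 0.05 = 1.05, or 14 × 0.05 = 0.70.

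**Correlated outcomes**

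The documents give no correlations, so a range is assumed. Under the null, each three-group omnibus statistic is approximately z₁² + z₂² (chi-square, 2 df), with p = exp(−(z₁² + z₂²)/2). A common correlation ρ was placed on the z values across outcomes. A simulation of 100,000 replicates and a direct numerical integration agree to within 0.003:

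| Assumed ρ | 21 tests | 14 tests | 8 levels alone |
|---|---|---|---|
| 0 | 0.66 | 0.51 | 0.34 |
| 0.3 | 0.56 | 0.44 | 0.30 |
| 0.5 | 0.44 | 0.36 | 0.26 |
| 0.7 | 0.31 | 0.26 | 0.20 |
| 0.8 | 0.24 | 0.20 | 0.16 |

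With 21 tests the rate reaches one half at ρ of about 0.4 (0.50).

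A less uniform structure was also tried for 21 tests: correlation 0.5 to 0.7 within a family of outcomes, 0.1 to 0.4 between families, and 0.8 to 0.9 between adjacent defocus levels. The rate was 0.43 to 0.56.

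**When some lens differences are real**

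Only truly null outcomes can give a false positive. Even with independence, 13 null outcomes give 1 − 0.95^13 = 0.487 and 14 give 0.512. The rate therefore passes one half only if at least 14 of the 21 are truly null.

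**The case against.** The strongest reply is that this is a retrospective case series whose documents separate primary from secondary outcomes and make no confirmatory claim for the latter. Leaving secondary outcomes unadjusted is common in such work, and the threshold is a generic sentence. That reply has force, but the text never says that secondary results are exploratory, and the generic sentence lets each be called significant. It also does not answer the missing defocus analysis.

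Four stronger readings are tempting, and the documents do not support them:

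- *A false lens difference is likely.* That needs 21 tests, an average correlation below about 0.4, and no true difference on most outcomes. Monocular and binocular acuities, the two refractions and neighbouring defocus levels come from the same patients and are probably correlated. The protocol's rationale also anticipates a broader range of clear vision with two of the lens types, so some differences are expected to be real.
- *The SAP tests the eight levels separately.* The eight levels are a measurement grid. Separate testing is an inference from the listed methods. The Analysis Population section refers to GEE for selected analyses, although only binocular UIVA is named later.
- *The plan treats secondary outcomes as confirmatory.* It does not say so. It only makes them eligible for the label significant.
- *The plan relies on defocus and halo/glare to separate the lenses.* The primary objective and outcomes rest that comparison on binocular uncorrected acuity and satisfaction.

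**Conclusion.** The point holds as a worthwhile improvement, not as a threat to the primary comparison. Two facts are fixed by the text: no error control operates across secondary outcomes, and the defocus curve has no stated analysis.

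The size is a range. If no lens differs on any secondary outcome, the chance of at least one false significant result is about 24% to 66% with 21 tests and about 20% to 51% with 14, for correlations from 0.8 down to 0. The correlation range is assumed, and real lens differences bring the rates down. The figures also assume that each test holds its nominal 5%. That would fail if both eyes entered the monocular and refraction tests as independent values, which the SAP does not settle.

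**What to change.** 1. **Defocus curve.** Analyse it in one GEE or mixed model clustered on patient, with lens, defocus level and lens-by-level terms.
   - Test lens and lens-by-level jointly, in a single test with 2 + 2 × 7 = 16 df. The interaction alone would miss a uniform shift between lenses.
   - Estimate lens contrasts at −1.50 D and −2.50 D, which correspond to the measured distances of 66 cm (1/0.66 = 1.52 D) and 40 cm (1/0.40 = 2.50 D). Apply Holm adjustment across the 3 pairs × 2 levels = 6 contrasts.
   - Show the other levels descriptively.
   - The study period ended in January 2024, so state that these levels were chosen after data collection.
2. **Significance Threshold section.** Restrict the term statistically significant to the primary outcomes. Report every secondary result, including the joint defocus test and its contrasts, as exploratory, with estimates and 95% confidence intervals.

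The cost is SAP wording, one additional model on data already collected (GEE is already in the plan), and the disclosure above. The downside is that fewer secondary differences can be labelled significant. Multiplicity across the six primary outcomes (three acuities and three satisfaction scores) is a separate issue that this change does not address.
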